The comparator in this study is placebo (0.9% saline), which will also be administered intravenously. The infusion will be a final volume of 100 mL given at an infusion rate of 1.67 mL/min over 60 minutes. Patients assigned to the placebo treatment group will receive multiple infusions of placebo during the treatment period according to the same schedule as the patients assigned to the AZ6765iv dose groups.

Duration of treatment

Eligible patients will have a screening period of up to 6 weeks. Following the screening period, patients will enter a 12-week double-blind treatment period and a 14-day follow-up period.

Outcome variables:

- **Efficacy**

Primary outcome variable:

- Change from baseline to Week 6 in the MADRS total score

Secondary outcome variables:

- Change from baseline to Week 12 in the MADRS total score
 - Percentage of patients with sustained response, defined as a $\geq 50\%$ reduction from baseline in the MADRS total score at Week 6 and which is maintained through Week 12
 - Change from baseline in the MADRS total score at each scheduled assessment
 - Percentage of responders at each scheduled assessment where responders are defined as patients with a $\geq 50\%$ reduction from baseline in MADRS total score
 - Percentage of patients who are remitted at each scheduled assessment where remission is defined as MADRS total score ≤ 8
 - Change from baseline in functional impairment at each scheduled assessment, as measured by the change from baseline in the SDS total score
 - Change in severity of depressive symptoms at each scheduled assessment as measured by change from baseline in the CGI-S score
 - Change in severity of depressive symptoms at each scheduled assessment as measured by the CGI-I response. Response in CGI-I is based on whether or not the CGI-I score is ≤ 2 (very much improved or much improved).
 - Change from baseline in self-rated severity of depressive symptoms at each scheduled assessment as measured by QIDS-SR-16 total score
- **Safety**
 - Adverse events (AEs)/serious adverse events (SAEs), including their severity
 - AEs leading to treatment discontinuation or study withdrawal

- Suicidality as measured by AEs of suicidality, suicidal ideation, suicide attempts, and suicide completion
- Other significant AEs (OAEs), other AEs of special interest
- Change from baseline in physical examination results, weight, body mass index (BMI), vital signs, clinical laboratory test results, and ECG results

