6.4.1 Definition of adverse events

An AE is the development of an undesirable medical condition or the deterioration of a pre-existing medical condition following or during exposure to a pharmaceutical product, whether or not considered causally related to the product. An undesirable medical condition can be symptoms (eg, nausea, chest pain), signs (eg, tachycardia, enlarged liver), or the abnormal results of an investigation (eg, laboratory findings, ECG). In clinical studies, an AE can include an undesirable medical condition occurring at any time even if no study treatment has been administered.

The term AE is used to include both serious and non-serious AEs.

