6.4.2 Definitions of serious adverse events

An SAE is an AE occurring during any study phase (ie, enrollment, treatment, washout, follow-up), that fulfills 1 or more of the following criteria:

- Results in death
- Is immediately life-threatening
- Requires in-patient hospitalization or prolongation of existing hospitalization
- Results in persistent or significant disability or incapacity or substantial disruption of the ability to conduct normal life functions
- Is a congenital abnormality or birth defect
- Is an important medical event that may jeopardize the patient or may require medical intervention to prevent one of the outcomes listed above

For reporting purposes, any suspected transmission via a medicinal product of an infectious agent is also considered an SAE and is reported in an expedited manner. Any organism, virus, or infectious particle (eg, prion protein transmitting Transmissible Spongiform Encephalopathy), pathogenic or non-pathogenic, is considered an infectious agent.

For further guidance on the definition of an SAE, see [Appendix B](#) to the CSP.

Psychiatric hospitalization is at times required and is expected for MDD. If hospitalization is needed due to the exacerbation of, or for the stabilization of, MDD, it will be reported as an SAE. The psychiatric assessments will reflect the worsening of the patient's condition and the need for hospitalization. These hospitalizations will be reported in the eCRF. Further guidance on the reporting of deterioration of the patient's condition with respect to MDD is contained in the following Section 6.4.3. If a patient is hospitalized, the AstraZeneca/ safety review group will decide if the patient is to be discontinued from

the study. Should the patient need to be discontinued from the study, all assessments and procedures required at Week 14 in [Table 4](#) will be conducted.

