6.4.3 Recording of adverse events

Time period for collection of adverse events

Adverse events and SAEs will be collected from the time of signature of informed consent throughout the treatment period and follow-up period. In patients who discontinue prior to final visit, unsolicited SAEs will be collected for 30 days post last study treatment.

Follow-up of unresolved adverse events

Any AEs that are unresolved at the patient's last AE assessment in the study are followed up by the investigator for as long as medically indicated, but without further recording in the eCRF. AstraZeneca or its representative retains the right to request additional information for any patient with ongoing AE(s)/SAE(s) at the end of the study, if judged necessary.

Variables

The following variables will be collected for each AE;

- AE (verbatim)
- The date and time when the AE started and stopped
- Maximum intensity or intensity or changes in intensity
- Whether the AE is serious or not
- Investigator causality rating against IP (yes or no)
- Action taken with regard to IP
- AE caused patient's withdrawal from the study (yes or no)
- Outcome

In addition, the following variables will be collected for SAEs:

- Date AE met criteria for SAE
- Date investigator became aware of SAE
- AE is serious due to
- Date of hospitalization
- Date of discharge

- Probable cause of death
- Date of death
- Autopsy performed
- Causality assessment in relation to study procedure(s)
- Causality assessment in relation to IP
- Causality assessment in relation to other medication
- Description of AE

Intensities will be reported for each AE in the following categories:

- Mild (awareness of sign or symptom, but easily tolerated)
- Moderate (discomfort sufficient to cause interference with normal activities)
- Severe (incapacitating, with inability to perform normal activities)

It is important to distinguish between serious and severe AEs. Severity is a measure of intensity whereas seriousness is defined by the criteria in Section 6.4.2. An AE of severe intensity need not necessarily be considered serious. For example, nausea that persists for several hours may be considered severe nausea, but not an SAE. On the other hand, a stroke that results in only a limited degree of disability may be considered a mild stroke, but would be an SAE.

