Worsening symptoms of the primary study condition (ie, MDD) should not be recorded as an AE. However, if hospitalization results from worsening psychiatric symptoms, the hospitalization should be recorded as an SAE in the eCRF.

Study drug abuse is an SAE, even when there are no symptoms or additional AEs, and should be reported according to the guidelines in Section 6.4.4. Misuse of IP is an AE, but is not considered an SAE unless accompanied by serious sequelae.

Should an overdose of IP occur, it must be reported in accordance with the procedures described in Section 13.2. An overdose associated with symptoms must be reported as an AE, while an overdose without associated symptoms, must be reported only on the separate AstraZeneca Clinical Study Overdose Report Form.

Suicidality

Any patient who, based on the investigator's judgment, poses an imminent risk of suicide should be discontinued from the study (see Section 5.8 and Section 5.9). All efforts should be taken to minimize the risk of suicide and the investigator should carefully monitor the

patient. If during the course of the study, a patient shows evidence of serious suicidality (for example warranted by a scoring of 4 or 5 on the C-SSRS), the patient should be referred to their attending psychiatrist, a local emergency room etc. for further evaluation to see if they are safe to continue in the study. The site should have the ability to direct any patient that requires emergency hospitalization to an emergency room or inpatient psychiatric unit that is within a 50 mile radius of the site. In addition, the patient should be able to contact someone at the site 24 hours per day should they have serious worsening of their condition.

Suicide and attempted suicide, irrespective of the method, but occurring in connection with the use of IP, should be reported as AEs (serious or nonserious). This event should be identified as suicide or attempted suicide, and the method of the suicide or attempt should be provided. If an attempted suicide meets the criteria for an SAE, the event must be reported according to the guidelines in Section 6.4.4. Strong suicidal thoughts should also be regarded as AEs.

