6.4.4 Reporting of serious adverse events

All SAEs have to be reported, whether or not considered causally related to the IP, or to the study procedure(s). All SAEs will be recorded in the CRF.

If any SAE occurs in the course of the study, then investigators or other site personnel inform appropriate AstraZeneca representatives within one day ie, immediately but **no later than the end of the next business day** of when he or she becomes aware of it.

The designated AstraZeneca representative works with the investigator to ensure that all the necessary information is provided to the AstraZeneca Patient Safety data entry site **within one calendar day** of initial receipt for fatal and life threatening events **and within 5 calendar days** of initial receipt for all other SAEs.

For fatal or life-threatening adverse events where important or relevant information is missing, active follow-up is undertaken immediately. Investigators or other site personnel inform AstraZeneca representatives of any follow-up information on a previously reported SAE within one calendar day ie, immediately but **no later than the end of the next business day** of when he or she becomes aware of it.

Once the investigators or other site personnel indicate an AE is serious in the WBDC system, an automated email alert is sent to the designated AstraZeneca representative.

If the WBDC system is not available, then the investigator or other study site personnel reports a SAE to the appropriate AstraZeneca representative by telephone. The AstraZeneca representative will advise the investigator/study site personnel how to proceed.

The reference document for definition of expectedness/listedness is the IB for the AstraZeneca drug AZD6765.

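### Section 6.4.3 ties AE reporting of suicide and attempted suicide to an undefined connection with the investigational product, at odds with the protocol's own AE rules

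*Protocol*

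**What the plan says.** The Suicidality paragraph of protocol Section 6.4.3 says that suicide and attempted suicide, "irrespective of the method, but occurring in connection with the use of IP, should be reported as AEs", and it names both serious and nonserious events. Later in the same paragraph, strong suicidal thoughts are to be regarded as AEs, with no condition about IP.

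The general rules carry no such condition:

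- Section 6.4.1 defines an AE "whether or not considered causally related to the product" and adds that in clinical studies "an AE can include an undesirable medical condition occurring at any time even if no study treatment has been administered".
- Section 6.4.2 begins its definition: "An SAE is an AE occurring during any study phase".
- Section 6.4.3 sets the window: "Adverse events and SAEs will be collected from the time of signature of informed consent throughout the treatment period and follow-up period". It lists the investigator's yes/no causality rating as a variable collected on each AE.
- Section 6.4.4 requires every SAE to be reported regardless of causality.
- Section 5.9 asks patients who discontinue after at least one dose to keep returning, with AEs and the C-SSRS among the assessments at each visit.

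The synopsis lists as a safety outcome: "Suicidality as measured by AEs of suicidality, suicidal ideation, suicide attempts, and suicide completion". Section 12.2.4 summarizes the incidence of suicidality AEs descriptively.

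**The concern.** An event-specific sentence that is narrower than the general rule invites a site to follow the specific one. Here the narrower sentence covers the most important psychiatric safety events in a severely depressed population. If an investigator must first decide that an attempt is connected with IP before recording it, a causality or exposure judgement comes ahead of the record. The protocol otherwise makes that judgement afterwards, in a separate field. Whether an attempt reaches the AE table could then depend on how each of about 60 sites reads an undefined phrase.

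**Working it through.** The protocol gives no figure to reproduce on this point, so the check sets its provisions side by side.

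**1. Specific rule against general rules.** Section 6.4.1 removes both causality and exposure as conditions for an AE. The Suicidality sentence adds a condition that must be one or the other. In the same paragraph, ideation is an AE unconditionally while an attempt is an AE conditionally, so the graver event has the narrower rule.

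**2. What the qualifier could mean.** It is not defined, and two readings are open.

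- *Causal.* Section 6.4.3 (Causality collection) classes deterioration of the study disease from lack of effect as not reasonably attributable to IP. An attempt put down to the depression would then fail the condition. This makes causality a test for recording, although the protocol elsewhere rates it on AEs already recorded.
- *Temporal.* Attempts in screening, or after IP has stopped, would fall outside. Yet the collection window starts at consent, and Section 5.9 keeps collecting AEs after discontinuation. Section 6.4.3 itself calls for patients at imminent suicide risk to be discontinued, so some high-risk patients would move into the time this reading leaves out.

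Neither reading agrees with the general rules.

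**3. What is captured anyway.** A completed suicide results in death and is an SAE. An attempt that is life-threatening, leads to admission or is otherwise medically important is also an SAE. Sections 6.4.2 and 6.4.4 bring these in regardless of cause. What remains is the nonserious attempt that a site judges unconnected with IP.

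**4. Whether another route brings that attempt into the AE count.**

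- Section 6.4.3 goes on to require monitoring of all suicidality events, with separate eCRF pages. The duty to send detailed accounts, however, is worded for AEs, so it can be read as starting only once the event has been accepted as one.
- The C-SSRS is given at screening and at every scheduled visit (Section 6.4.9.6). But Section 6.3.2 makes signs and symptoms found during ratings AEs only if they are serious or lead to stopping IP, so a C-SSRS finding does not automatically become an AE. The derived C-SSRS behavior variable in Section 11.2.6.1 is worded as running only to Week 3, although Section 12.2.4 summarizes the scale at each assessment.
- Section 6.4.3 also says that worsening symptoms of the study condition, and events clearly attributable to disease progression, are not AEs. Appendix F lists a suicide attempt within the ninth symptom of a Major Depressive Episode. A site could lean on that combination.

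**5. Where an omission would show.** Section 12.2.4 counts events from the day of randomization. An omitted attempt after randomization, on or off IP, would be missing from the tabulated incidence. An omitted attempt in screening would be missing from the record, but it would not have entered that rate.

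**6. Size.** An undercount would equal the number of nonserious attempts multiplied by the share judged unconnected with IP and left unrecorded. The protocol gives neither term, so no number follows.

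**The case against.** The best defence is that the sentence does not exclude anything. It says that events connected with IP use are reported as AEs; it does not say that others are not. A reader might infer an only-when rule, or a causal filter, but the word only is absent and the phrase may mean no more than during the period of use. This stands: the documents support an ambiguous, inconsistent qualifier and not an express prohibition.

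Second, the text that follows covers all suicidality events without reference to IP and even reaches accidents where suicidal intent cannot be ruled out. With SAE reporting and the C-SSRS, most of what matters is recorded somewhere. This stands in large part and is why the gap is narrow. It does not close the gap, for the reasons in step 4.

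Third, the disease-progression rule is aimed at worsening depression, and suicidality has its own heading. That is the better reading, but the protocol does not state it.

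Fourth, a reader might try to size the problem from expected dropout: 14% by Week 6 plus a further 10% by Week 12 is 24%, and 0.24 × 282 = 67.7, about 68 patients. Sections 12.2.6 and 12.3 give those rates as dropout for missing-data and sample-size purposes. They do not say how many patients will be observed off IP, and some will refuse further visits. At most, 68 is a ceiling on expected dropouts who could be seen off IP, relevant only under the temporal reading. It says nothing about how many attempts occur.

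Finally, the affected summary is descriptive and no hypothesis test depends on it. That is correct and limits the consequence.

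**Conclusion.** The qualifier in the Suicidality paragraph is undefined and inconsistent with Sections 6.4.1, 5.9 and 6.4.4 and with the rest of Section 6.4.3. The consequence is a possible omission, confined to nonserious attempts that a site judges unconnected with IP: in screening, after IP is stopped, or attributed to the depression. It requires a site to let this sentence override the general rules. A reader might conclude that suicidality AEs will be undercounted; the document shows only that they may be, and by an amount it does not allow anyone to calculate. Completed suicides and serious attempts are not at issue, and neither is any efficacy result. Because the affected count is a named safety outcome and the correction is simple, the provisions should be reconciled.

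**What to change.** In the Suicidality paragraph of Section 6.4.3, delete the qualifier about connection with IP, so that every suicide and suicide attempt from informed consent to the end of follow-up is recorded as an AE or SAE. Leave relation to IP to the causality field already collected on each AE. Add one sentence stating that neither the disease-progression exclusion in Section 6.4.3 nor the rating-scale exclusion in Section 6.3.2 applies to suicide or suicide attempts. This changes event recording only and does not touch patient management. It costs one deleted phrase, one added sentence and a few more AE records.

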6.4.4 Reporting of serious adverse events

All SAEs have to be reported, whether or not considered causally related to the IP, or to the study procedure(s). All SAEs will be recorded in the CRF.

If any SAE occurs in the course of the study, then investigators or other site personnel inform appropriate AstraZeneca representatives within one day ie, immediately but **no later than the end of the next business day** of when he or she becomes aware of it.

The designated AstraZeneca representative works with the investigator to ensure that all the necessary information is provided to the AstraZeneca Patient Safety data entry site **within one calendar day** of initial receipt for fatal and life threatening events **and within 5 calendar days** of initial receipt for all other SAEs.

For fatal or life-threatening adverse events where important or relevant information is missing, active follow-up is undertaken immediately. Investigators or other site personnel inform AstraZeneca representatives of any follow-up information on a previously reported SAE within one calendar day ie, immediately but **no later than the end of the next business day** of when he or she becomes aware of it.

Once the investigators or other site personnel indicate an AE is serious in the WBDC system, an automated email alert is sent to the designated AstraZeneca representative.

If the WBDC system is not available, then the investigator or other study site personnel reports a SAE to the appropriate AstraZeneca representative by telephone. The AstraZeneca representative will advise the investigator/study site personnel how to proceed.

The reference document for definition of expectedness/listedness is the IB for the AstraZeneca drug AZD6765.

6.4.5 Laboratory safety assessment

Blood and urine samples for determination of clinical chemistry, hematology, and urinalysis parameters will be taken at the times given in the study assessments (Table 4).

The clinical laboratory tests that will be assessed are listed in Table 7. The date and time of each collection will be recorded on the appropriate source documentation and eCRF.

Table 7 Laboratory assessments

Hematology	Clinical chemistry	Urinalysis
B-Hemoglobin	S-Creatinine	Specific gravity
B-Leukocyte (white blood cell) differential count	S-Uric acid	pH
B-Platelet count	S-Total bilirubin (direct and indirect)	Glucose

Table 7 Laboratory assessments

Hematology	Clinical chemistry	Urinalysis
B-Hematocrit	S-Albumin	Protein
B-Red blood cells	S-Alkaline phosphatase	Ketones
	S-ALT	Blood/hemoglobin
Other	S-AST	Leukocytes
HIV ^a	S-Potassium, S-Calcium, S-Sodium	Nitrates
HBsAg ^a	S-Chloride	Bilirubin
HCV ^a	S-Bicarbonate	Urobilinogen
HgbA _{1c}	S-Glucose	Urine osmolality
	Blood urea nitrogen (BUN)	Microscopic examination (if the urine dipstick is abnormal for leukocytes or blood; urine electrolytes [Na ⁺ , K ⁺ , Cl ⁻ , Ca ²⁺] will be determined as well)
	Protein	
	Lactate dehydrogenase (LDH)	Urine drug screen^b
	Lithium	Cocaine
	FSH ^a	Cannabinoids
		PCP
	S-Thyroid function tests	Amphetamines class, including methamphetamine
	Free triiodothyronine	Benzodiazepines class
	Free thyroxine	Barbiturates class
	TSH	Opiates class
		Propoxyphene
	S-β-hCG pregnancy test	Methaqualone ^c
		Methadone
		Ethanol
		Urine for β-hCG pregnancy test

ALT alanine transaminase; AST aspartate transaminase; β -hCG beta human chorionic gonadotropin; BUN blood urea nitrogen; HBsAg hepatitis B surface antigen; HCV hepatitis C virus; HDL high density lipoprotein; HgbA_{1c} glycosylated hemoglobin; HIV human immunodeficiency virus; LDH lactate dehydrogenase; LDL low density lipoprotein; PCP phencyclidine.

- ^a Blood sampling for FSH will be conducted for all post-menopausal women under 50 years of age at screening only.
- ^b HIV, HBsAg, HCV, and urine drug screen will be conducted at the screening visit only.
- ^c Methaqualone testing will be conducted in South Africa only via a local laboratory.

Prefix: B for blood and S for serum.

For UDS, patients can be re-tested only if either the initial THC, opiate, or barbiturate result is positive and they have a prescription, but the patient should be excluded if the result is still positive at the second test. The retest of opiates should occur after a 2-week washout. Patients with positive UDS for a drug(s) legally available by prescription must provide evidence of prescription for the drug(s).

Samples should be taken by adequately trained study personnel and handled in accordance with given instructions. Volumes of blood samples are described in Section 7.1. The central laboratory (see Section 13.1) will perform all clinical laboratory determinations as listed in Table 7. Up-to-date reference lists will be provided during the study and laboratory results will be compared with the laboratory standard normal ranges and flagged if they are outside the normal range. The investigator should make an assessment of the available results with regard to clinically significant abnormalities. If the laboratory value is outside the normal range and clinically meaningful, it should be followed until resolution or until the investigator considers no further follow-up necessary. The paper copy should be signed and archived in the eCRF and is the source data for laboratory variables at the site.

Blood samples for laboratory assessments will be collected from patients in a non-fasting state.

NB. In case a patient shows an AST **or** ALT $\geq 3 \times$ ULN **or** total bilirubin $\geq 2 \times$ ULN, please refer to Appendix E “Actions Required in Cases of Combined Increase of Aminotransferase and Total Bilirubin – Hy’s Law”, for further instructions.

